6.4.1 Co-Primary Efficacy Endpoints

The co-primary efficacy endpoints are PFS (as assessed by the investigator according to RECIST v1.1) and OS in the PAS.

PFS is defined as the time between the date of randomization and the date of first documented disease progression (as assessed by investigators according to RECIST v1.1) or death, whichever occurs first. Patients who have not experienced disease progression and have not died by the time of analysis will be censored at the time of the last tumor assessment. Patients with no post-baseline tumor assessment will be censored at the date of randomization.

OS is defined as the time between the date of randomization and death from any cause.

Data for patients who are not reported as having died by the date of analysis will be censored at the date when they were last known to be alive. Data for patients who do not have post-baseline information will be censored at the date of randomization.

PFS and OS will be compared between treatment arms with use of the unstratified log-rank test. The HR for PFS and OS will be estimated using both unstratified and stratified Cox proportional hazards model. The 95% CI for the HR will be provided.

[REDACTED]

The investigator-assessed PFS rates at 6 months and at 1 year and OS rates at 1 year, 18 months, and 2 years after randomization will be estimated using Kaplan-Meier methodology for each treatment arm, along with 95% CIs calculated using the standard error derived from Greenwood's formula. The 95% CI for the difference in PFS rates and OS rates between the two treatment arms will be estimated using the normal approximation method.

The timing of the final PFS analysis is described in Section 6.1.1 and the analysis timing for OS is described in Section 6.1.2.

6.4.2 Secondary Efficacy Endpoints

6.4.2.1 Progression-Free Survival and Overall Survival in the Full Analysis Set

PFS and OS in the FAS will be analyzed at the same time with the PAS, using the same methods as described in Section 6.4.1.

6.4.2.2 Objective Response Rate

A confirmed objective response is defined as either a confirmed CR or a PR, on two consecutive occasions \geq 4 weeks apart, as determined by the investigator using RECIST v1.1. Patients not meeting these criteria, including patients without any post-baseline tumor assessment, will be considered non-responders.

Confirmed ORR is defined as the proportion of patients who had a confirmed objective response. The analysis population for confirmed ORR will be the PAS and the FAS with measurable disease at baseline. An estimate of confirmed ORR and its 95% CI will be calculated using the Wilson score method for each treatment arm. CIs for the difference in confirmed ORRs between the two treatment arms will be determined using the Newcombe method.

6.4.2.3 Duration of Response

DOR will be assessed in patients who had a confirmed objective response as determined by the investigator using RECIST v1.1 in the PAS and the FAS. DOR is defined as the time interval from the date of the first occurrence of a confirmed objective response until the first date that progressive disease as determined by the investigator using RECIST v1.1 or death is documented, whichever occurs first. Patients who have not progressed and who have not died at the time of analysis will be censored at the time of last tumor assessment date. DOR is based on a non-randomized subset of patients (specifically, patients who achieved an objective response); therefore, formal hypothesis testing will not be performed for this endpoint. Comparisons between treatment arms will be made for descriptive purposes. The methodologies detailed for the PFS analysis will be used for the DOR analysis.

6.4.2.4 Patient-Reported Outcomes

TTCD in the PAS and the FAS for physical functioning and GHS using the EORTC QLQ-C30 is defined as the time from the date of randomization until the first confirmed clinically meaningful deterioration. Confirmed clinically meaningful deterioration for GHS and physical functioning is defined as a clinically meaningful decrease from baseline in GHS or physical functioning scale score that must be held for at least two consecutive assessments or an initial clinically meaningful decrease above baseline followed by death. A score change of ≥ 10 -point is considered to be clinically meaningful by patients for lung cancer-related symptoms, GHS and physical functioning subscale score (Osaba et al. 1998).

For TTCD, data for patients will be censored at the last time when they completed an assessment if they have not experienced a confirmed clinically meaningful deterioration event at the CCOD. If no baseline or post-baseline assessment is performed, patients will be censored at the randomization date. TTCD using the EORTC scale will be analyzed using the same methods as for PFS. Further details regarding the TTCD analyses for the EORTC measures will be described in the SAP.

Summary statistics (mean, SD, median, 25th and 75th percentiles, and range) and the mean change from baseline of linear-transformed scores will be reported for all of the items and subscales of the EORTC QLQ-C30 and EORTC IL46 (an item for troubled by side effects) questionnaires at each timepoint, the end of treatment, at the time of progression (per RECIST criteria), and at the time of clinical progression (if different from time to progression). In addition, mean scores for GHS, physical functioning, and selected symptom scales will be presented for the induction phase and the maintenance phase.

PRO-CTCAE data will be analyzed by treatment arm, the number (percentage) of patients reporting symptom by "frequency," "severity," "interference," and "presence" at each assessment. In addition, the frequency of symptoms will be cross tabulated with the severity of the symptom to explore the impact of the symptom when it occurred.

A summary table of the percentage of patients reporting severity of a symptom as 'severe' or 'very severe' over the course of the study by treatment arm will also be provided. Finally, a longitudinal analysis of change may be employed to understand how symptoms may have changed over the course of treatment.

Completion and compliance rates will be summarized at each timepoint by treatment arm.

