4.2 METHOD OF TREATMENT ASSIGNMENT AND BLINDING

4.2.1 Treatment Assignment

This is a Phase III, randomized, double-blind, placebo-controlled multicenter study. After written informed consent has been obtained and eligibility has been established, the study site will obtain the patient's identification number and treatment assignment from the interactive voice or web-based response system (IxRS).

Patients will be randomized to one of two treatment arms:

- Arm A: tiragolumab + atezolizumab + CE
- Arm B: placebo + atezolizumab + CE

Randomization will occur in a 1:1 ratio through use of a permuted-block randomization method to ensure that an approximately equal number of patients will be enrolled in each treatment arm within the baseline characteristics of the following stratification factors:

- ECOG Performance Status (0 vs. 1)
- LDH (\leq ULN vs. $>$ ULN)

Patients should receive their first dose of study drug on the day of randomization if possible. If this is not possible, the first dose should occur within 5 days after randomization.

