The questionnaires (EORTC QLQ-C30, EORTC IL46, PRO-CTCAE [select items], and EQ-5D-5L) will be completed during the induction phase at Cycle 1, Day 1 (baseline) prior to administration of study drug; then at every study treatment cycle prior to administration of study drug (i.e., on Cycle 2, Day 1; Cycle 3, Day 1; and Cycle 4, Day 1).

Starting at Cycle 5, the questionnaires will be completed at every other study treatment cycle prior to administration of study drug (i.e., on Cycle 5, Day 1; Cycle 7, Day 1; Cycle 9, Day 1; and so forth), and at the study treatment discontinuation visit (see [Appendix 1](#)).

Patients who discontinue study treatment for any reason other than radiographic disease progression per RECIST v1.1 (e.g., toxicity, symptomatic deterioration) will complete the EORTC QLQ-C30, PRO-CTCAE (select items), and EQ-5D-5L at each tumor assessment visit until radiographic disease progression per RECIST v1.1, death, loss to follow-up, consent withdrawal, or study termination by the Sponsor, whichever occurs first. Patients who continue to receive treatment after the confirmation of disease progression per RECIST v1.1 will complete the questionnaires at every other study treatment cycle until study treatment discontinuation.

During survival follow-up, for patients with radiographic disease progression per RECIST v1.1, the PRO questionnaires will be completed at 3 months (\pm 30 days) and 6 months (\pm 30 days) following the visit in which progressive disease was confirmed. For patients who continued treatment after disease progression per RECIST v1.1, PRO questionnaires will be completed at 3 months [\pm 30 days] and 6 months [\pm 30 days] following the study treatment discontinuation visit.

Patients whose native language is not available with the questionnaires are exempted from completing all PRO assessments.

The Sponsor will not derive adverse events reports from PRO data.

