6. STATISTICAL CONSIDERATIONS AND ANALYSIS PLAN

This is a Phase III, randomized, double-blind, placebo-controlled, multicenter study designed to evaluate the efficacy and safety of tiragolumab plus atezolizumab and CE compared to placebo plus atezolizumab and CE as 1L treatment in patients with chemotherapy-naïve ES-SCLC. The study is not powered to demonstrate statistical significance in terms of efficacy, and no formal hypothesis testing will be performed. More details of the analyses will be provided in the Statistical Analysis Plan (SAP).

The analyses of PFS and OS will be performed in the PAS and the FAS. Patients will be grouped according to the treatment assigned at randomization, regardless of whether they receive any assigned study drug. Confirmed ORR will be analyzed in patients within the PAS and the FAS who have measurable disease at baseline. DOR will be assessed in patients who have a confirmed objective response in the PAS and the FAS. TTCD analyses, mean scores and mean change from baseline analysis on PROs will be performed in the PAS and the FAS.

Safety analyses will be conducted in all randomized patients who received at least one dose of study treatment. Safety analyses will be performed by treatment arm and will be based on actual treatment received. Specifically, a patient will be included in the tiragolumab plus atezolizumab arm in the safety analyses if the patient receives any amount of tiragolumab, regardless of the initial treatment assignment at randomization.

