6.1 DETERMINATION OF SAMPLE SIZE

The primary objective of this study is to enroll approximately █ patients in the PAS in order to characterize the efficacy profile of tiragolumab plus atezolizumab. Assuming a 15% prevalence of presence or history of brain metastases at baseline, approximately 128 patients in total will be randomized in this study.

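### Two descriptive PRO summaries, the phase means and the cumulative PRO-CTCAE severity table, make no use of the Cycle 1 Day 1 form in the readable plan

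*Protocol*

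**What the plan says.** **The two summaries.** Protocol 6.4.2.4 plans a table of the "percentage of patients reporting severity of a symptom as 'severe' or 'very severe' over the course of the study by treatment arm". For the QLQ-C30 it adds that "mean scores for GHS, physical functioning, and selected symptom scales will be presented for the induction phase and the maintenance phase". Neither sentence says whether the pre-dose form is included, how the forms within a phase are averaged, or whether the result is adjusted for baseline.

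**When forms are completed.** Under Protocol 4.5.9.1 the questionnaires "will be completed during the induction phase at Cycle 1, Day 1 (baseline) prior to administration of study drug", then at Cycles 2, 3 and 4. After that: "Starting at Cycle 5, the questionnaires will be completed at every other study treatment cycle prior to administration of study drug". There is a form at treatment discontinuation. Patients who stop for reasons other than progression continue at tumor-assessment visits, and patients who have progressed complete forms 3 and 6 months later.

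**Where baseline is used.** Section 6.4.2.4 also reports change scores for all QLQ-C30 and IL46 items and subscales at each timepoint, and defines TTCD against the patient's own baseline. PRO-CTCAE percentages are planned at each assessment, and a longitudinal analysis of change is optional.

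**Status.** Protocol Section 6 states: "The study is not powered to demonstrate statistical significance in terms of efficacy, and no formal hypothesis testing will be performed". SAP Section 5 gives the SAP precedence over the protocol for a regulatory filing, but its section on patient-reported outcomes (5.5.1) is blacked out. This point therefore rests on the readable protocol.

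**The concern.** Protocol 3.4.6 wants patients' symptom reports to complement the evaluation of tolerability. A count that includes symptoms present before the first dose partly measures the disease. The plan handles investigator-reported events differently: a preexisting condition is an adverse event only if it worsens (Protocol 5.3.5.9), and SAP 5.6.2 counts events that start or worsen after first dosing. The cumulative PRO-CTCAE table has no matching rule, so the two tolerability displays are not on the same footing.

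A percentage ever severe also depends on how many forms each patient completes, which partly follows time on treatment. If one arm stays on treatment longer, its percentage can rise with no difference in risk per form.

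For the phase means there are two issues: a pre-dose form may be averaged into induction, and an arm comparison of raw means gives up precision that a baseline covariate would supply from data already collected. Since nothing is formally tested, readers will rely on these descriptive displays.

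**Working it through.** The documents state no precision or power figure for any PRO analysis, so there is nothing to reproduce. The nearest figure is the total: "approximately 128 patients in total will be randomized in this study". With "Assuming a 15% prevalence of presence or history of brain metastases at baseline", 128 × 0.85 = 108.8, so a PAS of about 109; the PAS number itself is redacted. "Randomization will occur in a 1:1 ratio" gives about 64 per arm in the FAS. SDs, correlations, symptom rates and treatment-duration ratios below are assumptions.

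**1. Pre-dose form in the induction mean.** Induction has four scheduled forms, one of them pre-dose. Randomization makes the expected arm difference zero on that form. For a constant on-treatment difference of 10 points, the equally weighted mean difference is (0 + 10 + 10 + 10)/4 = 7.5, a 25% loss. This needs no assumption about correlation, only equal averaging of all four forms.

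**2. Precision of an arm difference.** With n = 64 per arm, the 95% half-width is 1.96 × SD × √(2/n) for raw means. Multiply by √(2(1 − ρ)) for change scores and by √(1 − ρ²) for ANCOVA, where ρ is the correlation between baseline and follow-up.

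| SD | ρ | Raw | Change | ANCOVA | ANCOVA vs raw |
|---|---|---|---|---|---|
| 20 | 0.3 | 6.93 | 8.20 | 6.61 | 5% narrower |
| 20 | 0.5 | 6.93 | 6.93 | 6.00 | 13% narrower |
| 20 | 0.7 | 6.93 | 5.37 | 4.95 | 29% narrower |
| 25 | 0.3 | 8.66 | 10.25 | 8.26 | 5% narrower |
| 25 | 0.5 | 8.66 | 8.66 | 7.50 | 13% narrower |
| 25 | 0.7 | 8.66 | 6.71 | 6.19 | 29% narrower |

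The percentages do not depend on n, so they apply to the PAS as well. Change scores beat raw means only when ρ exceeds 0.5, so the planned change tables do not reliably recover the lost precision.

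**3. Symptoms severe before dosing.** Let b be the share severe at Cycle 1 Day 1, counted in both arms, and let 30% vs 20% be the rates among the rest. Each arm shows b + (1 − b) × rate:

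- b = 5%: 33.5% vs 24.0%, difference 9.5, ratio 1.40
- b = 10%: 37.0% vs 28.0%, difference 9.0, ratio 1.32
- b = 20%: 44.0% vs 36.0%, difference 8.0, ratio 1.22

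Without baseline-severe patients the difference is 10 and the ratio 1.50. If the pre-dose form is not counted but a share s of these patients report severe symptoms later, the same in both arms, the b × s terms cancel. The difference is again (1 − b) × 10.

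**4. Unequal form counts.** As an illustration, take exponential time on treatment with a control median of 5.2 months (the PFS median cited for this regimen in Protocol 1.2, used as a proxy) and hazard ratios of 0.77 or 0.70 for Arm A. Count post-baseline on-treatment forms plus the discontinuation form: the mean is about 7.6 in Arm B and 9.3 or 10.0 in Arm A. With k forms and the same per-form risk p in both arms, the ever-severe percentage is the mean of 1 − (1 − p)^k.

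- Forms independent, p = 3-10%: spurious excess of 3.5-5.4 points (0.77) or 4.8-7.3 points (0.70).
- Within-patient correlation 0.4, p = 5-10%: 1.0-1.8 or 1.4-2.3 points.
- Equal time on treatment: zero.

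Forms completed after discontinuation are not modelled.

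**The case against.** The strongest reply is that these are two supplementary displays in a plan that otherwise uses baseline. The change scores and TTCD are baseline-referenced, and the phase means are additional. Per-visit PRO-CTCAE percentages show the pre-dose level and compare arms without accumulating forms, while completion rates by timepoint and arm reveal unequal counts. No confidence interval or test is planned for the phase means, so the precision gain applies to an arm contrast that the plan does not specify. SAP 5.5.1 may already contain the missing rules. All of this stands, and it limits how much weight the point can carry.

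Four stronger readings should be resisted.

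- A reader might infer that the PRO analyses as a whole ignore baseline. Section 6.4.2.4 contradicts that.
- A reader might infer that the severity table expressly counts the pre-dose form. The text is silent; inclusion is only a natural reading of a whole-study count.
- A reader might infer that baseline symptoms bias the comparison. Under 1:1 randomization they dilute it and add chance imbalance, but do not tilt it in expectation.
- A reader might infer a large false difference from form counts. For example, 6 vs 8 forms at 3% each gives 1 − 0.97^6 = 16.7% vs 1 − 0.97^8 = 21.6%. Those inputs are assumed, and independent forms within a patient are implausible for symptoms.

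**Conclusion.** The point holds for two descriptive summaries in the readable protocol, subject to SAP 5.5.1.

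- **Phase means:** they carry no baseline adjustment, and the induction mean loses 25% of a constant on-treatment difference if all four forms are averaged equally.
- **Cumulative severity table:** it does not separate symptoms severe before dosing. A 10-point difference among patients not severe at entry appears as about 8-9.5 points at assumed baseline rates of 5-20%.
- **Form counts:** the effect is secondary, about 1-2 points under the correlated-forms illustration and nil if time on treatment is equal.

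No tested conclusion depends on any of this. It is an inexpensive improvement to how tolerability and quality of life will be read.

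**What to change.** Check SAP 5.5.1 first. If it has no such rules, specify the following.

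1. **Phase means.** Exclude Cycle 1 Day 1 from the induction mean. Report arm differences by visit or phase, with confidence intervals, from a repeated-measures model or ANCOVA with the Cycle 1 Day 1 score as covariate.
2. **Cumulative PRO-CTCAE table.** Count a severe or very severe score only if it is post-baseline and worse than the patient's own Cycle 1 Day 1 score. Show this alongside the planned per-visit percentages and state the denominator. Over all patients with a baseline form, and ignoring further worsening in patients already severe, the 10% example gives 0.90 × 30 = 27% vs 0.90 × 20 = 18%: the ratio returns to 1.50 but the difference stays at 9 points. Only a row limited to patients not severe at baseline shows the full 10.
3. **Common window.** This may be added as a sensitivity display, but it does not fully equalise form counts. Cycle 9 Day 1 falls 8 × 21 = 168 days after Cycle 1 Day 1, about 5.5 months, close to the cited 5.2-month median PFS, so many patients would stop before it closes.

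The cost is some protocol and SAP wording and a few tables, with no new data. Patients without a baseline form drop out of the adjusted tables, so their number should be shown by arm. PRO collection ran only to the 31 August 2023 cutoff (Protocol 4.5.9), so added tables should carry the date on which they were specified.

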6.5 SAFETY ANALYSES

Safety analyses will be conducted in all randomized patients who received at least one dose of study treatment.

Safety analyses will be performed by treatment arm and will be based on actual treatment received. Specifically, a patient will be included in the tiragolumab containing arm in the safety analyses if the patient receives any amount of tiragolumab, regardless of the initial treatment assignment at randomization.

Drug exposure will be summarized, including duration, dosage, and dose intensity.

Verbatim description of adverse events will be mapped to the MedDRA thesaurus terms. Severity for all adverse events will be graded by the investigator according to the NCI CTCAE v5.0, and severity for CRS will also be graded by the investigator according to the ASTCT consensus grading scale. All adverse will be summarized by treatment arm and NCI CTCAE grade. CRS will also be summarized by treatment arm and the ASTCT consensus grade. In addition, serious adverse events and adverse events leading to study treatment discontinuation or interruption will be summarized accordingly. Multiple occurrences of the same event will be counted once at the maximum severity. Laboratory data with values outside of the normal ranges will be identified. Additionally, selected laboratory data, including ADA results, will be summarized by treatment arm and grade. Vital signs will also be summarized by treatment arm and visit. Deaths and causes of deaths will be summarized.

Completion and compliance rates will be summarized at each timepoint by treatment arm. The analysis populations for PROs will be all randomized patients. The analysis populations for PRO changes will be all randomized patients with a non-missing baseline assessment and at least one non-missing post-baseline assessment.

6.6 PHARMACOKINETIC ANALYSES

Samples will be collected for PK analyses and to compare exposure in this study with that attained in previous studies. Serum concentrations of tiragolumab and atezolizumab will be reported as individual values and summarized (mean, standard deviation, coefficient of variation, median, range, geometric mean, and geometric mean coefficient of variation) by treatment arm and cycle, when appropriate and as data allow. Individual and median serum tiragolumab and atezolizumab concentrations will be

plotted by treatment arm and day. Tiragolumab and atezolizumab concentration data may be pooled with data from other studies using an established population-PK model to derive PK parameters such as clearance, volume of distribution, and AUC, as warranted by the data. Potential correlations of relevant PK parameters with safety, efficacy, or biomarker outcomes may be explored.

Schedule for collection of PK samples is outlined in [Appendix 2](#).

6.7 IMMUNOGENICITY ANALYSES

The immunogenicity analyses will include patients with any ADA assessments, with patients grouped according to treatment received.

The numbers and proportions of treatment-emergent ADA-positive patients and ADA-negative patients during both the treatment and follow-up periods for tiragolumab will be summarized by treatment arm.

The relationship between ADA status and safety, efficacy, and PK endpoints may be analyzed and reported via descriptive statistics.

